2.1 Background & Aims

Motion Minder Therapy (MoMT) is an innovative intervention, finely tuned to enhance fine motor skills in children facing the complexities of spastic hemiplegic cerebral palsy. MoMT propels forward by seamlessly integrating a unique blend of fine motor exercises and the incorporation of sensory cueing commercial watches. This intricately designed and tailored therapeutic approach holds the potential to reshape the landscape of fine motor skill development, emphasizing coordination and precision within a structured and engaging framework.

MoMT builds upon the successes of "Remind to Move Therapy," a methodology involving 5 to 6 hours of intervention to enhance upper extremity function with the therapist supervision. However, MoMT takes a significant leap forward by streamlining and targeting the intervention to a focused 1-hour duration with the therapist supervision. This strategic refinement aims to optimize the impact on fine motor skills in children with cerebral palsy.

Our futuristic therapy takes a pioneering leap by incorporating advanced sensory cueing mechanisms to augment the rehabilitation process. Leveraging the latest technology, we integrate commercial watches equipped with tactile vibrations and auditory alarms, as outlined in our meticulously crafted protocol.

The incorporation of tactile vibrations from commercial watches serves as a groundbreaking sensory cueing method. These vibrations are strategically designed to provide real-time feedback, enhancing proprioception and facilitating a more profound connection between the individual and their upper extremity functions. The tactile cues act as a guide, promoting a heightened awareness of body positioning and movement execution.

Simultaneously, auditory alarms emitted by the commercial watches introduce an additional layer of sensory stimulation. These alarms are synchronized with specific therapy milestones, creating a

dynamic auditory feedback system. This not only reinforces positive behaviours but also aids in the development of bimanual coordination, and unimanual dexterity. The integration of sound cues into our therapy protocol is a futuristic approach that transforms the rehabilitation experience, making it more engaging, responsive, and tailored to the individual's unique needs.

By merging cutting-edge technology with therapeutic principles, our approach not only addresses motor skills but also explores innovative avenues to enrich the sensory experience, paving the way for a more effective and immersive rehabilitation journey.

2.2 Background Literature Review

In a groundbreaking initiative, **Fong KN et al. (2013)** pioneered the concept of "Remind-to-Move Therapy," presenting the very first article on this innovative approach aimed at enhancing upper extremity motor function. This pioneering pilot study offers compelling proof-of-concept data, demonstrating the potential of a wearable device to serve as a reminder for children with cerebral palsy to engage in a predetermined set of arm exercises. The study's findings suggest that this novel approach holds promise for effectively promoting hemiplegic arm function, marking a significant stride forward in the integration of technology into therapeutic interventions for motor enhancement (1)

Various research has looked at the viability and safety of using tactile sensory cueing in a variety of situations, including chronic stroke survivors, with encouraging results. Investigating the effectiveness of combining this tactile cueing method with therapy to improve neurorehabilitation results is a logical next step in the research process ⁽²⁾.

In a pivotal study conducted by **Dong AQ et al. in 2016**, a groundbreaking revelation emerged: three weeks of 'Remind-to-Move' treatment proved to be instrumental in enhancing hemiplegic arm

function and increasing the quantity of hand use in children with unilateral cerebral palsy. This temporal intervention demonstrated immediate and tangible benefits, showcasing the potential of this innovative therapeutic approach. However, the study aptly points out that the exploration of long-term carryover effects remains an avenue for further investigation, underscoring the need for continued research to unveil the full scope and sustained impact of this promising intervention in the realm of paediatric rehabilitation ⁽³⁾.

Various convention interventions, such as the Hand-Arm Bimanual Intensive Therapy (HABIT) study by **Gordon AM et al.**, and Constraint-Induced Movement Therapy as studied by **Ramey SL et al.**, have demonstrated noteworthy success in enhancing motor function, surpassing conventional approaches. These therapeutic methods showcase a significant leap forward in improving motor skills, underscoring their potential to rehabilitation practices (4,5)

3. Study Protocol

3.1 Research Design Outline

The study aims to perform a pilot study on spastic hemiplegic cerebral palsy children in Aadhuraa Special School and Saveetha Medical College and Hospital.

Formerly titled "Effectiveness of Motion Minder Therapy (MoMT) Among Children with Spastic Hemiplegic Cerebral Palsy: A Pilot Study" involves children with spastic hemiplegic cerebral palsy children by using the Shriners Hospital Upper Extremity Evaluation ¹⁰. The outcome is the total score of the spontaneous functional analysis, dynamic positional analysis, and grasp/release analysis. Total scores of 45 for spontaneous functional analysis, 72 for dynamic positional analysis and 6 for grasp/release. Higher scores mean a better outcome.

3.2 Participants

Special school students from Aadhuraa Special School and Outpatient children from Saveetha Medical College and Hospital with spastic hemiplegic cerebral palsy will be eligible to participate in this study.

3.3 Recruitment

All children with spastic hemiplegic cerebral palsy attending Aadhuraa Special School and Saveetha Medical College and Hospital will be enrolled in the pilot stud. The participation information and consent sheet will be distributed to parents' which details including inclusion and exclusion criteria. Parents who agree to the investigation will be invited to undergo baseline assessments (Upper Limb Function - Shriners Hospital Upper Extremity Evaluation (SHUEE), Dexterity - Nine Hole Peg Test, Behavior - Strengths and difficulties questionnaire) All parents will have to return a signed consent form to the site principal investigator.

3.4 Administration

Time (Min)	Activity	Time	Sensory Cueing
		(Min)	Timing
0.00 To 05.00	Sticker Sorting	5 min	0.00
5.00 To 6.00	Rest & Reflection	1 min	-
6.00 To 14.00	Beads On Parade	8 min	06.00
14.00 To 16.00	Rest & Reflection	2 min	-
16.00 To 24.00	Pegboard Activities	8 min	16.00
24.00 To 26.00	Rest & Reflection	2 min	-
26.00 To 32.00	Sensory Bins	5 min	26.00

32.00 To 33.00	Rest & Reflection	1 min	-
33.00 To 41.00	Sculpture Building	8 min	33.00
41.00 To 46.00	Rest	5 min	-
46.00 To 54.00	Finger Painting & Drawing	8 min	46.00
	with different tools		
54.00 To 55.00	Rest & Reflection	2 min	-
55.00 To 60.00	Musical Instrument Play	5 min	55.00

^{*}Min – Minutes

1. Sticker Sorting:

Sticker sorting involves using a variety of colourful stickers that differ in size, shape, and texture. The child is encouraged to sort and place stickers onto corresponding shapes or categories. This activity enhances fine motor skills, hand-eye coordination, and cognitive abilities through visual discrimination.

2. Beads on Parade:

Beads On Parade involves threading colourful beads onto strings or wires to create vibrant patterns or jewellery. This activity targets fine motor coordination, bilateral hand use, and visual-motor integration. It fosters improved dexterity and hand strength while encouraging creativity.

3. Pegboard Activities:

Pegboard activities consist of arranging and securing pegs into a board with corresponding holes. Children can create various designs or replicate given patterns, promoting precision, hand strength, and spatial awareness. This activity enhances both fine motor skills.

4. Sensory Bins:

Sensory bins are containers filled with materials that engage different senses, such as touch and sight. Children explore and manipulate items like rice, beans, or textured objects, stimulating sensory perception and improving tactile sensitivity. This activity also encourages hand exploration for fine motor skills and sensory integration.

5. Sculpture Building:

Sculpture building involves using materials like clay or playdough or clay to create three-dimensional shapes and structures. This activity enhances fine motor skills, hand strength, coordination and creativity. Children with hemiplegic cerebral palsy can benefit from practicing bilateral hand use and refining their grasp patterns.

6. Finger Painting & Drawing with Different Tools:

Finger painting and drawing involve creating art using various tools like paintbrushes, sponges, or even fingers. This activity enhances fine motor skills, hand control, and creativity. Offering a range of tools accommodates different grip strengths and preferences, allowing children to explore their artistic abilities.

7. Musical Instrument Play:

Musical instrument play involves using instruments such as Mini Guitar, Maracas and Xylophone. Children are encouraged to use both hands to produce different sounds and rhythms. This activity promotes bilateral coordination, fine motor control, and sensory integration through auditory and tactile experiences.

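### Do the two mismatched rows in the section 3.4 session table require a change to the plan?

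*Combined protocol and SAP*

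**What the plan says.** Section 2.1 presents the therapy as a shortened form of an earlier, longer method: "streamlining and targeting the intervention to a focused 1-hour duration with the therapist supervision". Section 3.4 lays out that hour in a 13-row table of seven activities and six rest periods. Each row has a clock interval and a duration, and each activity also has a cue time.

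The two rows at issue are "26.00 To 32.00 Sensory Bins 5 min 26.00" and "54.00 To 55.00 Rest & Reflection 2 min". The rows that follow them fix where their intervals end: "32.00 To 33.00 Rest & Reflection 1 min" and "55.00 To 60.00 Musical Instrument Play 5 min 55.00".

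Section 3.1 describes a "pilot study on spastic hemiplegic cerebral palsy children in Aadhuraa Special School and Saveetha Medical College and Hospital". Sections 4.1 and 4.2 analyse the Shriners Hospital Upper Extremity Evaluation, the Nine Hole Peg Test and the Strengths and Difficulties Questionnaire by a one-group repeated measures ANOVA over four time points.

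**The concern.** The table is the only minute-by-minute account of the session in the document, and it cannot be followed literally in every column. The document does not say whether the interval or the duration takes precedence. A check of the total will not find the slip, because both columns add to 60.

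Timing matters in principle. Section 2.1 ties the alarms to points in the session, and the one-hour format is the feature said to distinguish this therapy from its predecessor. Children come from a school and a hospital. If the two settings read the table differently, they would deliver slightly different sessions, and a report of activity and rest time would need a choice between columns. Accumulating the durations would also move the start of two activities away from their printed cues.

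**Working it through.** **Inputs.** All come from the section 3.4 table, except the one-hour session length, which is in section 2.1.

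**Step 1: reproduce the plan's own total.**

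- Clock intervals (end minus start): 5 + 1 + 8 + 2 + 8 + 2 + 6 + 1 + 8 + 5 + 8 + 1 + 5 = 60 min.
- Listed durations: 5 + 1 + 8 + 2 + 8 + 2 + 5 + 1 + 8 + 5 + 8 + 2 + 5 = 60 min.

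Both give the stated hour.

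**Step 2: compare row by row.**

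| Row | Interval | End minus start | Listed | Listed minus interval |
|---|---|---|---|---|
| Sensory Bins | 26.00–32.00 | 6 | 5 | −1 |
| Last Rest & Reflection | 54.00–55.00 | 1 | 2 | +1 |
| Other 11 rows | – | – | – | 0 |

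The net difference is −1 + 1 = 0, which is why the totals agree.

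**Step 3: split activity from rest.**

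| | Activity | Rest | Activity share of 60 min |
|---|---|---|---|
| Clock | 5 + 8 + 8 + 6 + 8 + 8 + 5 = 48 | 1 + 2 + 2 + 1 + 5 + 1 = 12 | 48/60 = 80.0% |
| Listed | 5 + 8 + 8 + 5 + 8 + 8 + 5 = 47 | 1 + 2 + 2 + 1 + 5 + 2 = 13 | 47/60 = 78.3% |

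The difference in activity time is 1 minute, or 1/48 = 2.1%.

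**Step 4: check the cues.** The printed cues are at 0, 6, 16, 26, 33, 46 and 55 minutes. The printed activity starts are the same seven values, so cue minus start is 0 in all seven. The 13 intervals also run from 0.00 to 60.00 with no gap or overlap.

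If the printed clock times are set aside and the durations accumulated, the activities start at 0, 6, 16, 26, 32, 45 and 55. Two cues then fall 1 minute after the start of their activity: "33.00 To 41.00 Sculpture Building 8 min 33.00" (33 − 32 = 1) and "46.00 To 54.00 Finger Painting & Drawing 8 min 46.00" (46 − 45 = 1). If each row keeps its printed start but runs for its listed duration, Sensory Bins ends at 26 + 5 = 31, leaving 31.00–32.00 empty, and the last rest ends at 54 + 2 = 56, overlapping the final activity from 55.00. Both results are the same two mismatched cells carried forward, not further errors.

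**Step 5: look for a use of these figures in the analysis.** The section 3.5 outcomes are scores or completion times measured at baseline and weeks 4, 8 and 12. The ANOVA in sections 4.1 and 4.2 has one factor, time, with four levels. Session minutes are not an outcome, a covariate or an adherence criterion, and the missing-data rule in section 4.3 does not use them.

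**The case for a change.** The strongest case for acting is that the contradiction is definite and sits in the only detailed description of the intervention. A therapist who times activities from the duration column has no warning that the clock column differs. The repair is one small table correction, so there is little reason to leave it.

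Much of this stands. The mismatch is real: both rows are intact in the text and their neighbours confirm the interval ends. The document states no rule of precedence, and which figure was meant in each row is for the sponsor to say.

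The inference that the trial is put at risk does not stand. The clock and cue columns agree with each other throughout, so a workable session can be read from the table as printed. Nothing in the document suggests that the two settings would read it differently. No section plans to report the split between activity and rest. The document also gives no number of sessions, so total activity time could not be derived from either column. Once the two cells agree, a statement of which column governs would be redundant, and a record by site of which column was used would be out of proportion to one minute.

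**Conclusion.** This is a clerical slip: two of 13 rows differ by 1 minute each, in opposite directions. It shifts 1 minute between activity and rest (48 and 12, or 47 and 13) within a session that lasts 60 minutes on either column. The sponsor should reconcile the two rows when the document is next edited; this review takes no position on which figures are intended.

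No change to the design, outcomes or analysis follows. Every planned estimate and p-value is computed from assessment scores at four visits, so correcting the table would leave the planned calculations as they are. With one group, there is no between-arm contrast that a 1-minute difference in delivery could bias.

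The conclusion rests on two conditions. The first is that session minutes are not used as an exposure or adherence variable, and none is planned. The second is the judgement that a shift of 1 minute in 60 between activity and rest would not materially alter a child's scores; the document gives no dose-response figure with which to test that.

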3.5 Assessment & Outcomes Measures

3.5.1 Primary outcomes

- Shriners Hospital Upper Extremity Evaluation (SHUEE)
 - The Shriners Hospital Upper Extremity Evaluation is a video-based tool for the assessment of upper extremity function. The outcome is the total score of the spontaneous functional analysis, dynamic positional analysis, and grasp/release analysis.
 - Total scores of 45 for spontaneous functional analysis, 72 for dynamic positional analysis and 6 for grasp/release. Higher scores mean a better outcome.
 - o [Time Frame: Baseline, 4th week, 8th week, 12th week]

• Nine Hole Peg Test

- Nine Hole Peg Test is used to measure the dexterity. Scores on nine-hole peg test are measured in seconds, indicating time taken to complete task.
- Higher scores indicate worse outcome, as they show slower completion times and reduced dexterity.
- o [Time Frame: Baseline, 4th week, 8th week, 12th week]

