4.1 Primary Outcomes

The primary analyses will find effect i) pilot group guidelines on their mean and standard deviation: (i) Shriners Hospital Upper Extremity Evaluation (SHUEE), (ii) Nine Hole Peg Test. P-values <0.05 will be considered statistically significant.

1*4-Repeated measures analysis of variance (ANOVA) will be performed to test the effectiveness in the intervention between the time intervals (baseline, mid-intervention, post-intervention, and follow-up).

The post–hoc analysis will be conducted to investigate significant effect within the time intervals. Condition on if the sphericity violated (p-value < 0.05), the Greenhouse-Geisser estimated correction will be applied.

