4.3 Missing Data

For children who do not attend the assessment, the mean imputation of the assessment scores from their allocation group will be used.

5. Informed Consent Forms (ICF)

Written consent will be gained from the parents of children with spastic hemiplegic cerebral palsy using the consent forms attached to the application.

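### Does the plan need a rule for a child who attends but cannot finish the Nine Hole Peg Test?

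*Combined protocol and SAP*

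**What the plan says.** Section 3.5.1 defines the peg test score with one sentence, "Scores on nine-hole peg test are measured in seconds, indicating time taken to complete task", and gives its direction: "Higher scores indicate worse outcome, as they show slower completion times and reduced dexterity". It sets no time limit, ceiling value, partial score or code for an unfinished attempt, and it does not name the hand tested. The test is scheduled four times ("Time Frame: Baseline, 4th week, 8th week, 12th week").

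Section 4.1 makes it one of two primary outcomes ("i) Shriners Hospital Upper Extremity Evaluation (SHUEE), (ii) Nine Hole Peg Test") and specifies the test: "1*4-Repeated measures analysis of variance (ANOVA) will be performed to test the effectiveness in the intervention between the time intervals".

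Section 4.3 is the only missing-data rule: "For children who do not attend the assessment, the mean imputation of the assessment scores from their allocation group will be used". Its trigger is absence from the assessment.

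Section 3.3 enrols all children with the diagnosis at the two sites. It says the parents' sheet carries the eligibility criteria ("which details including inclusion and exclusion criteria"). That sheet is not in the text available.

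**The concern.** A completion time exists only if the task is completed. In children with a hemiplegic upper limb, some might not manage it at one or more visits. Such a child has no score under 3.5.1 and does not trigger 4.3. A one-group, four-visit repeated measures ANOVA needs all four values, so one unfinished test would remove the child from every visit. Had the same child stayed at home that day, 4.3 would have kept the child in with the group mean.

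Two things would be at stake. First, the dexterity result would describe only children who finish at all four visits, and a child who moves from unable to able would contribute nothing. Second, an analyst who wanted to keep these children could pick a rule after seeing the data, and the candidate rules can give different answers.

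**Working it through.** The documents give no sample size, SD, effect size or non-completion rate, so there is no figure of the plan's own to reproduce. Every input below is an assumption unless a section is named.

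**1. The gap.** Sections 3.5.1, 4.1 and 4.3 taken together contain no rule for an attended but unfinished test. As a check on the consequence, a standard within-subject ANOVA routine (statsmodels) refused data with one of a child's four values missing, and ran once that child was removed.

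**2. How many children could be lost.** Let q be the share unable to finish at any one visit, independent across visits. The share with all four times is (1 − q)^4:

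- q = 5%: 0.95^4 = 81.5%
- q = 10%: 0.90^4 = 65.6%
- q = 20%: 0.80^4 = 41.0%

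With 20 children enrolled (assumed), about 16, 13 and 8 remain. Independence is the pessimistic end. If the same children fail every time, the loss is close to q itself.

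**3. Whether the handling matters.** Take ten invented children. Eight finish at baseline in 40, 45, 50, 55, 60, 70, 80 and 90 s (mean 61.25) and at week 12 in 38, 43, 48, 52, 57, 66, 75 and 85 s (mean 58). Their changes sum to −26 s. Two cannot finish at baseline but finish at week 12 in 140 and 150 s. Mean change:

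- Left out: −26/8 = −3.25 s
- Group mean at baseline: (−26 + 78.75 + 88.75)/10 = +14.15 s
- Ceiling of 180 s: (−26 − 40 − 30)/10 = −9.6 s
- Ceiling of 300 s: (−26 − 160 − 150)/10 = −33.6 s

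The handling can change the sign. The positive value comes from the group mean, which section 4.3 does not extend to children who attend. It would also give a very slow performer an average time, against the direction of the scale in 3.5.1.

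**4. Simulation of the SAP's ANOVA.** The setting was n = 15, baseline median 40 s, 15% gain by week 8, within-child error of 15% or 6 s, Greenhouse-Geisser applied when sphericity is rejected, and 10,000 replicates per cell.

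*Children above a time limit that 5 / 10 / 20% exceed at baseline:*

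| Handling | Type I error | Power |
|---|---|---|
| Left out | 4.1-5.0% | 64-69 / 62-66 / 55-58% |
| Scored at the limit | not quoted | 66-72 / 66-72 / 62-69% |
| Group mean | 4-6 / 6-9 / 14-17% | not quoted |

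This setting does not represent the plan's power. Section 3.5.1 has no limit, so a child slower than the implied limits (about 57-109 s) simply records a long time and stays in. A rerun with 3,000 replicates compared no limit with a limit plus exclusion at the 20% share. Power was 72-73% against 55-57% under constant error. Under proportional error it was 64% against 50% with between-child log SD 0.4, and 50-52% against 49-56% with log SD 0.6. These differences are the effect of imposing a limit and excluding, not of the text as it stands.

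*One or two children truly unable until week 8, then finishing in 60-100 s.* This does match the concern. Power:

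- Left out: 64-69%
- Ranks, with an unfinished test as slowest: 66-81%
- Ceiling of 120 s: 48-91%
- Ceiling of 180 s: 0-46%
- Ceiling of 300 s: 0%
- Group mean: 0-30%

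*One to three children gain or lose the ability, others unchanged.* Leaving them out gives a mean change of 0.0 s, with 4-5% of trials significant. Ranks give 5-12%. At this size, only a count by visit shows what happened to these children.

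**5. Would a written rule improve the result?** Writing exclusion into the plan reproduces the literal reading, so the primary result is the same. A ceiling makes the answer depend on the seconds chosen. Ranks do better in the truly-unable setting. In the time-limit setting they lose 3-11 points of power against exclusion under constant error, and differ by −4 to +4 points under proportional error. A child unable at all four visits gives four tied ranks and says nothing about change.

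**The case for a change.** The strongest case for a change is that the peg test is a primary outcome, the gap can be checked line by line, and in the truly-unable setting the same data give power from 0% to about 90% depending on a rule that nobody has written down. An eligibility criterion might screen out such children at baseline, but it would not score an unfinished test at weeks 4, 8 or 12. A few sentences before data are seen would settle it. In a pilot, the number of children who cannot do a primary test is itself worth knowing.

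Much of this stands. The text is silent, the candidate rules are not equivalent, and a count of unfinished tests belongs in any competent report. The step from there to a defect does not stand. The extremes of that range belong to ceiling or group-mean scores, which no section prescribes for a child who attends. The handling that follows from the text is exclusion, which keeps the type I error near its nominal level. The contrast with 4.3 is untidy, but it does not push the analyst towards a biased result, because 4.3 is limited to absence. What is left is recording, reporting and an optional sensitivity analysis.

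**Conclusion.** No change follows. The plan omits a detail that analysts can fill sensibly: treat an unfinished test as having no time in seconds, leave that child out of the ANOVA, and say how many were left out and at which visits. Going further is a trade-off among exclusion, a ceiling and ranks, and the documents give no basis for calling one of them correct.

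If every child finishes, nothing changes. If some do not, the primary dexterity result covers those who finish at all four visits. The type I error under exclusion is 4.1-5.0% in simulation (4.1-5.4% in an independent repeat with 1,500 replicates per cell). The loss of power cannot be sized from the documents. The one quoted comparison that posits truly unable children and a real gain in the others puts exclusion at 64-69% and ranks at 66-81%.

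This rests on assumed values for the sample size, variability, gain and share unable to finish. It also rests on reading 4.3 as written, for absent children only. Using the group mean for a child who attended would depart from the plan and would be a fault in the analysis, not in the document.
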